7.2 Secondary Objectives

[figure not shown]
- Evaluate the safety and tolerability of leuprolide acetate 45 mg for injectable suspension in children with CPP
- Characterize the burst kinetics of leuprolide acetate 45 mg after the first administration
- Characterize the pharmacodynamic (PD) relationship of leuprolide serum concentrations to concentrations of serum LH, FSH and to testosterone/estradiol
- Assess percent changes in height velocity and bone age progression after the first administration
- Assess changes in physical signs of puberty as measured by changes in Tanner stages or in changes or onset of menses
- Determine the dosing interval (5 or 6 months) at which leuprolide acetate is able to suppress LH concentration to <4 mIU/mL (after GnRHa stimulation test), as data permit

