enter Part B extension. Injections #3 and #4 will be administered in 5-month intervals after Injection #2 in Part A. The dosing interval will be dependent on emerging data from Part A. Subjects will return to the clinic periodically up to approximately an additional 10 months from start of Part B for efficacy, safety and PK assessments.

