8.6.7 Part A, Visit 5 (~Month 6/Week 24 ± 7 days)—Injection #2

Predose:

1. Query subject or parent: “How have you felt in the last two weeks?” or “How has your child felt in the last two weeks?” Complete [Table 4](#)
2. Vital signs - measured prior to any blood draws
3. AE and concomitant medications assessments
4. Physical Examination—directed
5. Tanner stage
6. Height and weight
7. X-ray of non-dominant hand and wrist
8. Clinical laboratory assessments (hematology, chemistry) as per [Appendix 13.1](#)
9. Urine for urinalysis, performed using dipstick supplied by Sponsor

10. Urine pregnancy test, females only

NOTE: Results must be negative prior to receiving Injection #2

11. Blood samples for basal LH, FSH, testosterone/estradiol concentrations PRIOR to the GnRHa stimulation

12. Blood sample for basal serum leuprolide concentrations PRIOR to the GnRHa stimulation

13. GnRHa stimulation: aqueous leuprolide acetate 20 µg/kg body weight administered SC

14. Blood samples for LH, FSH, testosterone/estradiol concentrations 30 ± 5 minutes AFTER the GnRHa stimulation

Study Drug Administration:

15. Pharmacy - prepare study drug for injection (see Pharmacy Manual for complete instructions)

a. Remove kit from refrigerator, at least 30 minutes prior to planned administration and allow the study drug to reach room temperature

b. Start mixing process with the product kit within ≤ 30 minutes prior to the injection time.

16. Apply topical or local anesthetic (per Investigator discretion) to injection site prior to planned injection time; record medication, dose, route, and time

17. Administer second injection of study drug

Postdose:

18. Final AE assessment prior to subject discharge from clinic

19. Schedule/confirm next visit

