8.6.12 Part B, Visit 7 (~Month 11/Week 44 ± 7 days)—Injection #3

The decision to conduct Part B extension of the study will be based on the results of the interim analysis (see [Section 9.2.4](#)).

Predose:

1. Informed consent and assent (may be signed up to 28 days prior to Part B, Visit 7)
2. Query subject or parent “How have you felt in the last two weeks?” or “How has your child felt in the last two weeks?” Complete [Table 4](#)
3. Vital signs - measured prior to any blood draws
4. AE and concomitant medications assessments
5. Physical Examination—directed

6. Tanner stage
7. Height and weight
8. X-ray of non-dominant hand and wrist
9. Clinical laboratory assessments (hematology, chemistry)
 - a. Hematology and chemistry parameters as per [Appendix 13.1](#)
 - b. Serum lipids, fasting for ≥ 8 hours (water permitted)
10. Urine for urinalysis, performed using dipstick supplied by Sponsor
11. Urine pregnancy test, females only
NOTE: Results must be negative prior to receiving Injection #3)
12. Blood samples for basal LH, FSH, testosterone/estradiol concentrations PRIOR to the GnRH α stimulation
13. Blood sample for basal serum leuprolide concentrations PRIOR to the GnRH α stimulation
14. GnRH α stimulation: aqueous leuprolide acetate 20 $\mu\text{g}/\text{kg}$ body weight administered SC
15. Blood samples for LH, FSH, testosterone/estradiol concentrations 30 \pm 5 minutes AFTER the GnRH α stimulation test

Study Drug Administration:

16. Pharmacy - prepare study drug for injection (see Pharmacy Manual for complete instructions)
 - a. Remove kit from refrigerator, at least 30 minutes prior to planned administration and allow the study drug to reach room temperature
 - b. Start mixing process with the product kit within ≤ 30 minutes prior to the injection time.
17. Apply topical or local anesthetic (per Investigator discretion) to injection site prior to planned injection time; record medication, dose, route, and time
18. Administer third injection of study drug

Postdose:

1. Final AE assessment prior to subject discharge from clinic
2. Schedule/confirm next visit

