### **5.2. Secondary Objectives**

The secondary objectives of this study are to:

- Evaluate the safety and tolerability of leuprolide acetate 45 mg for injectable suspension in children with CPP;
- Characterize the burst kinetics of leuprolide acetate 45 mg after the first administration;
- Characterize the pharmacodynamic (PD) relationship of leuprolide serum concentrations to concentrations of serum luteinizing hormone (LH), follicle stimulating hormone (FSH) and testosterone/estradiol;
- Assess percent change from baseline in height and bone age after the first treatment administration;
- Assess growth velocity of height in cm/year after the first treatment administration;
- Assess changes in physical signs of puberty as measured by changes in Tanner stages or in changes or onset of menses; and
- Determine the dosing interval (5 or 6 months) at which leuprolide acetate is able to suppress LH concentration to <4 mIU/mL (after gonadotropin releasing hormone agonist [GnRHa] stimulation test) as data permits.

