 GnRHa (SC) stimulation must be performed AFTER a blood sample has been collected for measurement of basal LH, FSH AND testosterone/estradiol concentrations and prior to study drug injection. Blood samples for LH, FSH and testosterone/estradiol concentrations must be obtained again 30 ± 5 minutes after SC administration of GnRHa. See Section 8.1.14.

Part A	Screening	Injection #1					Injection #2				End of Treatment 	Unscheduled Visit (PI discretion)
Visit Number:		Visit 1	Telephone Contact 1	Visit 2	Visit 3	Visit 4	Visit 5	Telephone Contact 2	Visit 6	Visit 7	Visit 8	
Scheduled Day/Week	Within 28 days	Baseline (Day 0)	Week 2 ± 2 days	Week 4 ± 7 days	Week 12 ± 7 days	Week 20 ± 7 days	Week 24 ± 7 days	Week 26 ± 2 days	Week 36 ± 7 days	Week 44 ± 7 days	Week 48 ± 7 days	
Scheduled Month (approximate)		--	~Month 0.5	~Month 1	~Month 3	~Month 5	~Month 6	~Month 6.5	~Month 9	~Month 11	~Month 12	
LH and FSH samples 30 ± 5 min AFTER GnRH a stimulation	X				X		X		X		X	X
Testosterone/estradiol samples 30 ± 5 min AFTER GnRH a stimulation	X				X		X		X		X	X
Study drug (leuprolide acetate) SC injection 		X					X					
Adverse Events Assessment		X		X	X	X	X		X	X	X	X
Schedule/Confirm Next Visit	X	X		X	X	X	X		X	X		(X)

 Local or topical anesthetic may be used at the discretion of the Investigator, prior to study drug administration. Name of the anesthetic used, route, and time of dose must be recorded.

Table 2 Blood Sampling Times by Parameter for Visit 1—Part A

Visit Number—Part A	Visit 1			
Scheduled Day/Month	Baseline (Day 0)			
	Time relative to injection			
	≥30 min prior	1 h (±5 min)	4 h (±10 min)	6 h (± 15 min)
LH and FSH samples	X	X	X	X
Testosterone/estradiol samples	X	X	X	X
Serum Leuprolide	X	X	X	X

Vital signs to be measured BEFORE any blood draws.

Table 3 Schedule of Assessments—Part B

Part B	Injection #3			Injection #4			End of Treatment	Unscheduled Visit (PI discretion)
Visit Number:	Visit 7	Telephone Contact 3	Visit 8	Visit 9	Telephone Contact 4	Visit 10	Visit 11	
Scheduled Day/Week	Week 44 ± 7 days	Week 46 ±2 days	Week 60 ± 7 days	Week 64 ± 7 days	Week 66 ±2 days	Week 76 ± 7 days	Week 80 ± 7 days	
Scheduled Month (approximate)	~Month 11	~Month 11.5	~Month 15	~Month 16	~Month 16.5	~Month 20	~Month 21	
Written Informed Consent / Assent 	X							
Complete Physical Examination							X	X
Query Subject: How have you felt in last 2 weeks?	X	X	X	X	X	X	X	X

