4) Serum concentrations will be analyzed by evaluating concentration at each time point using continuous descriptive analysis; and by evaluating the PK parameters AUC, Cmax and Tmax using continuous descriptive analysis. Since the PK sampling frequency in this trial is limited due to the age of the subjects, it will be expected that the PK parameters will have larger intra-patient variability. Concentration plots in the original and log scale will be created, combined over subjects and by subject. Continuous descriptive analysis will be provided for absolute values of AUC, Cmax and Tmax as well as log transformed values of these parameters. All together the above analyses in part or whole will be referred to as *PK analysis*.

Because this study collects data at many interim time points, extensive use of graphs to display categorical descriptive analysis results and continuous descriptive analysis results over time will be employed. This will facilitate an assessment of trend.

Further note that because tables containing categorical descriptive analysis and continuous descriptive analysis will exist for the various outcome parameters at each time point, selected time points of interest can be compared to each other for a specific purpose. For example, the medical writer can compare descriptive outcomes at visits after injection 2 to visits after injection 4 to evaluate GnRHa simulation results under a six and a five month injection separation schedule. Using specific comparisons of descriptive statistics at designated time points, objectives for the assessment of efficacy (see Protocol Section 9.2.2: Efficacy Evaluations) can be accommodated.

Plots of individual subject outcomes will be generated for all variable concentrations used in the PK/PD analyses (Leuprolide, LH, FSH, testosterone and estradiol concentration), bone age and height.

The table that follows summarizes the planned analyses for baseline, efficacy, safety and PK variables.

Table 5 Type of Analysis Applied to Baseline, Efficacy, Safety and PK Variables

Variable Class	Variable(s)	Analysis				Listed/Not Analyzed 	Time Points Analyzed (Visits) 
		Categorical Descriptive Analysis	Continuous Descriptive Analysis	Shift Table Analysis	PK Analysis		
Baseline	Presence of Informed Consent	x					Screening, Visit 7
Baseline	Inclusion/Exclusion Criteria	x					Screening
Baseline	Demographics (categorical)	x					Screening

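### In children who enter Part B, the SAP's example contrast of five- and six-month schedules contains no test taken six months after a dose

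*SAP*

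**What the plan says.** A secondary objective in Protocol Section 7.2 is to "Determine the dosing interval (5 or 6 months) at which leuprolide acetate is able to suppress LH concentration to <4 mIU/mL" after stimulation. SAP Section 5.2 repeats it, and both documents add that this is as far as the data permit.

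On how to address it, SAP Section 7 explains that descriptive tables will exist at every time point, so chosen time points can be set against each other. It gives an illustration, worded as an option: "For example, the medical writer can compare descriptive outcomes". The comparison it then describes is of "visits after injection 2 to visits after injection 4 to evaluate GnRHa simulation results under a six and a five month injection separation schedule" (stimulation is evidently meant).

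The dosing schedule comes from the protocol:
- Injection 2 is given at the visit headed "Part A, Visit 5 (~Month 6/Week 24 ± 7 days)—Injection #2".
- Section 8.1 states that "Injections #3 and #4 will be administered in 5-month intervals after Injection #2 in Part A".
- Injection 3 is therefore given at the visit headed "Part B, Visit 7 (~Month 11/Week 44 ± 7 days)—Injection #3", and Injection 4 at Month 16 (Week 64).

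A footnote to SAP Table 1 places each stimulation test after sampling for basal hormone "concentrations and prior to study drug injection". Another footnote to that table says that children who continue into Part B skip Part A Visit 7 and the Part A end-of-treatment visit (Visit 8, Month 12).

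**The concern.** A contrast that uses visits after Injection 4 can be made only if Part B is invoked. In that case the interval after Injection 2 is five months, like the later ones. The group of visits that the SAP associates with six months then contains no observation at six months.

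Part B is triggered when stimulated LH is below 4 mIU/mL in fewer than 85% of the interim children at Month 6. The observation that shows whether suppression lasts six months is the Month 6 test, and the example leaves it out. A child who loses suppression between Month 5 and Month 6 could look suppressed at every test used for the six-month side. The comparison could then suggest that the two intervals perform alike when the data say otherwise.

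**Working it through.** No sample-size formula applies; the check is date arithmetic on the visit schedules (Protocol Tables 1 and 3, Sections 8.6.2 to 8.6.18; SAP Tables 1 and 3).

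**1. Gaps between injections**
- Injection 1 to 2: Week 24 − 0 = 24 weeks (6 months)
- Injection 2 to 3: Week 44 − 24 = 20 weeks (5 months)
- Injection 3 to 4: Week 64 − 44 = 20 weeks (5 months)

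The stated six- and five-month intervals reproduce.

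**2. Time since the last injection at each stimulation test (visit week − injection week)**

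| Test | Last injection | Weeks since dose | Months by label | Who has it |
|---|---|---|---|---|
| Visit 3, Week 12 | 1 | 12 − 0 = 12 | 3 | all |
| Visit 5 pre-dose, Week 24 | 1 | 24 − 0 = 24 | 6 | all who reach Month 6 |
| Visit 6, Week 36 | 2 | 36 − 24 = 12 | 3 | all who reach Month 9 |
| Part A Visit 8, Week 48 | 2 | 48 − 24 = 24 | 6 | only children who stay in Part A |
| Part B Visit 7 pre-dose, Week 44 | 2 | 44 − 24 = 20 | 5 | Part B only |
| Part B Visit 9 pre-dose, Week 64 | 3 | 64 − 44 = 20 | 5 | Part B only |
| Part B Visit 11, Week 80 | 4 | 80 − 64 = 16 | 5 | Part B only |

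**3. The example applied to a Part B child.** Visits after Injection 2 supply tests at 12 and 20 weeks; the visit after Injection 4 supplies one at 16 weeks (5 months by label). None is at 24 weeks. The one 24-week test, Visit 5, belongs to Injection 1.

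**4. Visit windows.** Each visit after Day 0 has a window of ±7 days. The Week 44 test can therefore be at most 20 + 2 = 22 weeks after Injection 2. The Month 6 test is at least 24 − 1 = 23 weeks after Injection 1. The windows do not close the gap.

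**5. Children who stay in Part A.** Their Month 12 test is a six-month value after Injection 2. How many there would be is uncertain. The plan's round numbers leave about 40 − 27 = 13 Month 6 completers outside Part B, not all of whom need reach Month 12. The entry rules also differ. Protocol Section 8.1.1 excludes children beyond Month 11. SAP Section 6.1.1 names only current children who have not had a second injection, which would leave the roughly 16 interim children in Part A. SAP Section 6.1.2 speaks of all subjects receiving Injections 3 and 4.

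**6. The Month 21 label.** Visits up to Month 16 run at four weeks per month (6 × 4 = 24, 11 × 4 = 44, 16 × 4 = 64). On that scale Month 21 would be 21 × 4 = Week 84, but the schedule gives Week 80. The text calls this visit five months after Injection 4; the week numbers make it 16 weeks, against 20 for the other five-month intervals.

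**The case against.** The strongest reply is that the sentence is an illustration: it says what the medical writer can do and fixes no analysis. This is right. So is the point that Month 6 is not lost. If Part B runs, the Month 6 result becomes a secondary outcome (Protocol Section 9.2.2, SAP Section 6.6). SAP Section 8.2.2 also reports suppression at every available measurement other than the primary one.

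A reader might infer from the example that no six-month value could enter the comparison at all, or that the plan discards its six-month data. The documents support neither. Children who finish under Part A have a Month 12 test 24 weeks after Injection 2, and the Month 6 table exists whatever the example says. But the Month 12 values come from different children than the Injection 4 values. Pooling them under visits after Injection 2 would mix 12-, 20- and 24-week tests.

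A second reply concerns wording. SAP Section 8.2.1 describes Part A as two injections six months apart and the two Part B injections as five months apart. If separation means the gap before the latest injection, the labels are literally correct. Even so, no test after Injection 2 in a Part B child is more than 20 weeks post-dose, so the contrast does not test suppression at six months.

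The objective is also qualified by what the data permit. Here the data do permit a better comparison, because the Month 6 test is already scheduled.

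**Conclusion.** The point holds for Part B participants. Of their two stimulation tests after Injection 2, none is at 24 weeks; the later is 4 weeks short. The only 24-week test in these children, at Month 6, is outside the example contrast.

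The size is limited: one optional sentence is wrong for its purpose, no data or planned table is missing, and the primary endpoint is unaffected. It still merits correction. Section 7 is the only place where the SAP says which visits stand for which schedule. Following it would hide the six-month failures that trigger Part B. SAP Section 4 also labels analyses outside the final SAP as post hoc, so the intended comparison is best named in advance.

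The conclusion assumes that Part B is invoked and that visits follow the schedule. It does not depend on how the Week 80 discrepancy is resolved, because the fault lies in the visits after Injection 2.

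**What to change.** In SAP Section 7, replace the example with a named comparison:
- The six-month value is stimulated LH below 4 mIU/mL at Visit 5 (Month 6).
- Compare it within child with the pre-dose tests at Months 11 and 16 and the end-of-interval test at Month 21. Paired yes/no tables in children with both tests would suffice and fit the descriptive plan.
- Show Month 12 separately for children who finish under Part A, and do not pool it with earlier tests after Injection 2.
- State that interval is confounded with injection number and time on treatment, so a difference cannot be attributed to interval alone.

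Before Month 21 is used as a five-month value, reconcile the Month 21 label with the Week 64 to Week 80 schedule in both documents. Aligning the Part B entry rules across the protocol and SAP would settle which children contribute Month 12.

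The change to the comparison costs SAP wording only, since every test it uses is already scheduled. Reconciling the Month 21 label and the entry rules may also require corrections to the protocol.

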## **8. BASELINE INFORMATION AND TREATMENT EMERGENT EFFICACY, PHARMACOKINETIC AND SAFETY ENDPOINTS**

Baseline, efficacy, pharmacokinetic (PK) and safety information to be collected as described below.

### **8.1. Baseline and Related Information**

Some baseline variables in the sub-sections to follow may also serve as efficacy, safety and PK endpoints when captured post treatment. In such instances, variables may be located in more than one section of this SAP.

The variables that will be used to characterize study subjects at baseline are presented below.

#### **8.1.1. Demographic Information**

Demographic characteristics will be collected, including date of birth, sex, race (*American Indian; or Alaska Native; Asian; Black or African American; Native Hawaiian or Other Pacific Islander; White*), and ethnicity (*Hispanic or Latino; Not Hispanic or Latino*).

#### **8.1.2. Medical History**

Relevant medical history will be collected including prior and ongoing medical illnesses, conditions, and surgical procedures within the 24 months prior to enrollment.

#### **8.1.3. Prior and Concomitant Medications and Treatments**

All prior and concomitant medications, as well as any diagnostic, therapeutic, or surgical procedures performed, will be recorded from the time of signing the ICF/Assent Form (if required) throughout the subject's participation in the study.

#### **8.1.4. Vital Signs**

Vital signs will be measured after the subject has been in a seated or supine position for 5 minutes. Vital sign assessments will include the measurement of blood pressure (mm Hg), heart rate (beats per minute), respiration rate (breaths per minute) and temperature (oral, tympanic, or temporal; °C or °F).

#### **8.1.5. Weight**

Body weight (kg) will be measured.

#### **8.1.6. Height**

Standing height will be recorded with a calibrated stadiometer (e.g., “Harpenden” stadiometer) that has increments in millimeters (mm) and a functional Frankfort Plane perpendicular to the standing surface. The Frankfort Plane will be used on the stadiometer to determine the actual standing height to  $\pm 1$  mm.

#### **8.1.7. Physical Examination**

A complete physical exam (PE) will be performed by study personnel who are qualified to perform such examinations. At a minimum, the PE should include the cardiovascular system, the respiratory system, and the abdomen.

Thereafter, a directed or targeted PE will be performed covering body systems related to the disease, including Tanner stages, and/or to assess any ongoing AEs.

#### **8.1.8. Tanner Stages and Menses**

Sexual development in puberty will be assessed by Tanner staging, a system developed by Marshall and Tanneriv to categorize pubertal maturation. See Appendix 1 for details on the Tanner stages. The presence of menses and any change in menses will be collected.

#### **8.1.9. Clinical Laboratory Assessments**

Clinical laboratory assessments (hematology, clinical chemistry, fasting serum lipids, hepatitis B & C, and urinalysis parameters) are listed in Appendix 2. Urinalysis assessments will be by “dipstick” assessments using urinalysis kits that will be provided to the sites by the Sponsor and evaluated locally. All other laboratory assessments will be from the blood samples collected at the appropriate assessment times and analyzed by a central laboratory.

#### **8.1.10. Pregnancy Test**

Urine pregnancy tests will be performed on female subjects. All female subjects must have a negative pregnancy test prior to receiving each injection of study drug. The pregnancy test will also be performed at End of Treatment in Part A or Part B extension (if invoked), and at the discretion of the Investigator.

#### **8.1.11. Hand and Wrist X-Ray (Bone Age)**

A single X-ray of the non-dominant hand and wrist will be obtained to determine bone age using a Greulich and Pyle Atlas. Although a local reader will determine study eligibility during screening, X-rays will be sent to a blinded central reader for the bone age evaluations that will be analyzed.

#### **8.1.12. Basal LH, FSH, Testosterone/Estradiol Concentrations**

Blood samples for serum LH, FSH, testosterone (males) / estradiol (females) concentrations (as appropriate) will be collected and analyzed by a central laboratory according to current validated

assays. All samples will be obtained before each study drug injection and before GnRHa stimulation tests. A central laboratory will be used.

### **8.1.13. Abbreviated GnRHa Stimulation Test**

Baseline blood samples for serum LH, FSH, and testosterone/estradiol concentrations will be obtained prior to the start of a GnRHa stimulation test. A standard dose of 20 µg/kg body weight of aqueous leuprolide acetate will be administered SC. Blood samples to measure serum LH, FSH and testosterone/estradiol concentrations will be obtained again 30 minutes later.

